### 3.5. Blinding

Participants cannot be blinded to intervention allocation. Assessors (RA at each site) who collect data, including administering questionnaires, will be unaware of the time at which the site transitions from GAE to PROPEL. While it is more likely that a given site will be allocated to GAE at the start of the study period, and to PROPEL at the end of the study, inclusion of two sites that always complete either GAE or PROPEL will create uncertainty in intervention allocation at all time points. Furthermore, using objective methods to collect data pertaining to the primary outcome (i.e., heart rate and activity monitor) helps to protect against bias if assessors inadvertently become unblinded.

### 3.6. Outcomes

[figure not shown]
#### 3.6.1. Primary outcomes – physical activity

Physical activity will be assessed using a step counter, heart rate monitor, and questionnaires for 7 continuous days at three time points: 1) one month, 2) four months, and 3) six months post-intervention (Figure 2). Because of the limitations of relying on a single method of data collection for physical activity data, combining data from these three sources is recommended. Participants will be supplied with a commercial wrist-worn step counter and heart rate monitor (FitBit Charge HR). Our pilot data suggests that this device provides reasonably accurate measures of walking activity and heart rate among individuals with stroke (unpublished data). Individuals who typically use a rollator for ambulation may also be provided with an activity monitor to be worn at the ankle (FitBit One), which would be more accurate for measuring walking activity than a wrist-worn device for these individuals. The devices will be configured to not provide participants with information regarding step counts and heart rate. While participants will not have access to activity data to reduce measurement bias, they may choose to purchase their own activity-monitoring device to augment self-management strategies. The devices will be mailed to participants with a postage-paid return envelope.

Participants will be instructed to wear the device at all times (except when bathing) for 7 days continuously (Appendix E).

The Physical Activity Scale for Individuals with Physical Disabilities (PASIPD) will be conducted by telephone with a blinded RA at the end of the 7-day monitoring period. The PASIPD is a 13-item questionnaire in which participants are asked to indicate the frequency and duration of recreational, household and occupational physical activities completed in the previous 7 days. The PASID has been validated within a group of individuals with various physical disabilities, including individuals with stroke, showing good test-retest reliability ( $\rho=0.77$ ) and criterion validity when compared to accelerometer-based activity monitoring ( $\rho=0.30$ ).

We will use the step activity, heart rate, and questionnaire data to determine if participants meet the recommended intensity and duration of physical activity in the community; that is, at least 150 minutes per week of moderate-vigorous intensity exercise. Participants will be deemed to meet the recommendations within a given week if they meet at least two of three criteria: 1) record at least 150 'active minutes' (from the step activity monitor); 2) record at least 150 minutes of heart rate between 55-80% of age-predicted maximum; and/or 3) report at least 150 minutes of moderate and/or vigorous intensity activity on the PASIPD.

**Figure 2: Hypothetical timeline for one participant.** The exact timing of in- and out-patient rehabilitation will vary for each participant. The sub-maximal aerobic capacity test is completed during in-patient rehabilitation. After this point the participant could participate in individual or open-group aerobic exercise during in- and out-patient rehabilitation (while waiting to be enrolled in the study intervention). The closed-group study intervention (group aerobic exercise (GAE) only or PROPEL) will likely start during out-patient rehabilitation, though some patients may start during in-patient rehabilitation. The participant will be enrolled in the study at the end of the study intervention, at which point cohort descriptors, the Short Self-Efficacy for Exercise (SSEE) scale, and the Short Outcome Expectations for Exercise (SOEE) scale will be collected. Activity monitoring will be conducted for 7 days continuously at three time points: 1) one month; 2) 4 months; 3) and 6 months after the end of the study intervention. The Barriers to Being Active Quiz (BBAQ) will be conducted at the 1-month post-intervention time point.

### 3.6.2. Secondary outcomes - self-efficacy and outcome expectations for exercise, and barriers to activity

Exercise self-efficacy will be assessed using the Short Self-Efficacy for Exercise (SSEE) scale. The SSEE is a four-item questionnaire where participants are required to rate their confidence exercising through pain and fatigue, and when alone and depressed on a five-point scale. The Short Outcome Expectation for Exercise (SOEE) scale will be used to assess beliefs and attitudes related to exercise. The SOEE is a five-item questionnaire where participants are asked to rate their beliefs regarding the benefits of exercise on a five-point scale. The SSEE and SOEE will be assessed at enrolment into the study. The SSEE and SOEE have been shown to be valid and reliable among individuals with chronic stroke.

Perceived barriers to physical activity will be assessed 1-month post-intervention with the Barriers to Being Active Quiz (BBAQ). The BBAQ has previously been used to evaluate barriers to exercise among individuals with stroke. The BBAQ is a 21-item scale where individuals are required to indicate how likely they are to make specific statements regarding barriers to exercise, for example “I’m getting older so exercise can be risky”. Items on seven categories of barriers are included in the questionnaire: lack of time, social influence, lack of energy, lack of willpower, fear of injury, lack of skill, and lack of resources. Each individual item is scored from 0-3 and scores for each barrier category are the sum of the scores for the three items in that category. Participants are considered to have a ‘significant’ barrier to being active if the score for a category is 5 or higher. The average number of significant barriers per participant will be calculated.

### 3.6.3. Cohort descriptors

The following information will be obtained from chart review in order to characterize individuals who participate in the study: age, sex, time post-stroke (at enrolment into the study), lesion location, and medical conditions/history (Appendix F). The National Institutes of Health Stroke Scale (NIH-SS), the Chedoke-McMaster Stroke Assessment (CMSA) foot and leg scores, and the Montreal Cognitive Assessment will be administered at enrolment into the study by the RA or study PT; however, if these measures were conducted as part of clinical care within 1-week of study enrolment, the scores will be extracted from the hospital charts to minimize participant burden. The NIH-SS is an 11-item scale that provides a gross measure of the effects and severity of stroke. The NIH-SS has good intra-rater (ICCs=0.93) and inter-rater (ICCs=0.95) reliability. The CMSA assigns a score according to the level of motor recovery in the foot and leg and is frequently used to evaluate level of motor recovery post-stroke in clinical settings. The CMSA foot and leg scores have good intra-rater (ICCs=0.94-0.98) and inter-rater (ICCs=0.85-0.96) reliability. The MOCA is a paper-based test that can be used to screen for mild cognitive impairment; patients are scored on visuospatial and executive function, naming, memory, attention, language, abstraction, delayed recall, and orientation.

We will document the frequency and intensity of exercise during in- and out-patient rehabilitation by chart review (Appendix F). Participants will complete a questionnaire at baseline that asks about their social supports, employment, familial responsibilities, living situation etc (Appendix G), which are factors that could influence participation in physical activity. Many of these questions have been adapted from the Canadian Longitudinal Study on Aging. Some questions will be repeated at the 6-month post-discharge time-point (Appendix H) to account for lifestyle changes since discharge from rehabilitation. Pre-morbid exercise behaviour will be evaluated with the Schmidt retrospective physical activity scale. This scale shows good agreement with previously-completed questionnaires regarding physical activity. We will use this scale to estimate participants’ average amount of time (hours/day) prior to their strokes spent in sedentary activities (e.g., watching television, sedentary occupational activity) and in physical recreational activity or exercise.

### 3.7. Intervention allocation

The time at which each site transitions from GAE to PROPEL will be determined by drawing site names at random (see Figure 1 for full details). One site will implement PROPEL at the start of the study period, whereas one site will never transition to PROPEL; this will help to ensure blinding of assessors (see next section). The site that does not transition to PROPEL during the study period will be offered training in PROPEL at the end of the study period. Intervention allocation will be performed at the start of the study period by the principal investigator, who will not be directly involved in recruiting or data collection.

### 3.8. Statistical analysis

We will compare cohort descriptors between the two phases (GAE and PROPEL) using t-tests, Mann-Whitney *U* tests, or chi-square tests, as appropriate. If phases significantly differ at baseline on cohort descriptors these measures may be used as covariates in the analysis. To test our primary hypothesis, we will compare the proportion of active and inactive individuals at the final assessment point (6 months post-intervention) using mixed-model logistic regression, with fixed effects of time and phase and random effect of cluster (site). We will also examine between-phase differences in physical activity at the 1-month and 4-month time points, which could reveal short-term benefits of PROPEL, even if there are no differences at 6-months. A similar mixed-model ANOVA will be used to compare SSEE, SOEE, and BBAQ scores between programs to test the secondary hypothesis.

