### 3.3. Interventions

The interventions will be implemented as part of routine care at all sites according to the schedule outlined in Figure 1 (e.g., Site B is expected to implement GAE in mid-February 2017, and PROPEL in around mid-May 2017). The interventions will supplement, rather than replace, current practice; that is, patients will still complete their regularly-scheduled physiotherapy, occupational therapy, and speech and language pathology sessions, as required. However, for patients who are enrolled in the GAE or PROPEL interventions, physiotherapists might choose to not complete individualized aerobic exercise during patients' regularly scheduled physiotherapy sessions as this will be completed as part of GAE/PROPEL, and to spend this time instead focusing on other rehabilitation goals (e.g., balance or gait retraining).

Both interventions involve supervised, individualized, group aerobic exercise up to 3 days/week for 6 weeks. Patients will be referred by their treating physiotherapist. The interventions will be implemented as part of routine care in out-patient rehabilitation at each site, and will be delivered in a 'closed group' format. That is, participants referred to the program will be placed on a waiting list until there are a sufficient number of participants to form a group ( $\geq 3$ ), and all participants in the group will start the program at the same time. This will ensure that the mean time post-stroke at study enrolment does not differ between the two phases of intervention. Prior to starting the group, participants may complete individualized or open-group aerobic exercise as part of their regular in- or out-patient rehabilitation.

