#### 3.3.1. Control intervention – GAE

The control intervention will involve group aerobic exercise only (GAE). The intensity and duration of exercise within a session will be determined from a sub-maximal aerobic capacity test conducted prior to entry into the program using a protocol developed by our team. The choice of exercise modality for the submaximal test and for training (e.g., recumbent stepper, cycle ergometer, or treadmill) will be individually prescribed based on patients' sensori-motor recovery, postural control, functional abilities, and safety. Group exercise will be supervised by the PT. A typical exercise session will involve a 3-5 minute 'warm-up', 20-30 minutes of aerobic exercise at a target heart rate determined from the submaximal test, and a 3-5 minute 'cool-down' of low-intensity exercise, which we have shown to be feasible for this target population. Heart rate, blood pressure, rate of perceived exertion, workload, and duration of training will be documented for each session. These data will be reviewed by the PT with appropriate progression of the intensity and/or duration of exercise as necessary.

Patients in the GAE program may receive general advice to keep physically active after discharge, and may receive an individualized home exercise program, as is currently routine care at all sites.

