Potential participants will be assessed for eligibility by the study PT within the final two weeks of the patients' participation in the GAE/PROPEL programs. The study PT, who is in the patients' circle of care, will ask eligible patients if they are interested in speaking with the RA about participating in the study. The RA will discuss the study at a time that is convenient for interested individuals. She will describe the study, as outlined in the consent form (Appendix A) and will answer any questions the patient may have about the study. The patient will be provided with a copy of the consent form and will be invited to discuss the study with friends or family members, and/or to take some time to think about being involved in the study. If a patient indicates that s/he would like to participate in the study, s/he will be asked to sign the consent form. At that time, the RA will arrange a time that is convenient for the participant to collect baseline data (see Section 3.6.3.). We will assume that patients who do not provide consent to the study within two weeks after they finish the GAE/PROPEL program are not interested in participating in the study.

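### Section 3.8 lets between-phase significance tests, plus analyst discretion, choose the covariates, so the primary model cannot be stated before the data are seen

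*Combined protocol and SAP*

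**What the plan says.** Section 3.8 opens with a screen: "We will compare cohort descriptors between the two phases (GAE and PROPEL) using t-tests", or with Mann-Whitney or chi-square tests where those fit better. None of these has a term for site or calendar period. The next sentence is the adjustment rule: "If phases significantly differ at baseline on cohort descriptors these measures may be used as covariates in the analysis". The primary model that follows is a logistic mixed model with time and phase as fixed effects and site as a random effect. It names no covariate. The section gives no screening threshold, does not say when a flagged descriptor must be used, and does not say whether the adjusted or the unadjusted result is primary.

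Four other places bear on what counts as a baseline descriptor:

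- Section 3.4, on the step after consent: "the RA will arrange a time that is convenient for the participant to collect baseline data (see Section 3.6.3".
- Figure 2 legend (Section 3.6.1): "The participant will be enrolled in the study at the end of the study intervention, at which point cohort descriptors" are collected.
- Section 3.6.3, among the cohort descriptors: "We will document the frequency and intensity of exercise during in- and out-patient rehabilitation by chart review".
- Section 3.3, on where the programs run: "The interventions will be implemented as part of routine care in out-patient rehabilitation at each site".

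**The concern.** A covariate earns its place in a model by predicting the outcome. A between-phase p-value does not measure that. Under this rule a prognostic variable that happens to be balanced is left out, and a non-prognostic one that happens to differ may be put in. The word 'may' then allows several models for the same data, none of them named as primary.

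The design makes the screen fire often. Figure 1 and Section 3.7 allocate whole sites: one delivers PROPEL throughout, one never does, and the other four contribute unequal shares to each phase. Ordinary differences between hospitals therefore appear as differences between phases, and a test without a site term treats them as if patients had been allocated one by one.

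The word 'baseline' also offers less protection than it normally would. Here it means enrolment around the end of the program, so a descriptor recorded then can include something that happened after allocation. At stake is whether the primary estimate comes from one model defined in advance and free of post-allocation variables.

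**Working it through.** **1. Sample sizes used.** Section 3.9 gives 96 per phase, and 120 with 20% drop-out. This reproduces: for 25% vs 50%, two-sided 0.05, 80% power and unpooled variance, n = 54.9 per phase. The design effect is 1 + (16 - 1) × 0.05 = 1.75, with 96/6 = 16 per site and phase. Then 54.9 × 1.75 = 96.1, and 96/0.80 = 120. The check below uses totals of 192 and 240.

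**2. Flag rate for one descriptor with no phase effect.** The plan gives no figure to reproduce here. Take a descriptor with total variance 1 and ICC ρ. Let n1 and n0 be a site's numbers in PROPEL and GAE, N1 and N0 the phase totals, and w = n1/N1 - n0/N0.

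- Variance the test assumes: k = 1/N1 + 1/N0.
- Actual variance of the phase difference: (1 - ρ)k + ρΣw².
- Ratio: R = (1 - ρ) + ρΣw²/k.
- Flag rate: f = 2[1 - Φ(1.96/√R)].

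Figure 1 gives PROPEL shares of 15, 12, 9, 6, 3 and 0 out of 15 groups. With six equal sites, w = ±1/3, ±1/5, ±1/15, so Σw² = 0.311.

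- Total 192: k = 0.02083. At ρ = 0.05, R = 0.95 + 0.05 × 0.311/0.02083 = 1.70 and f = 13.2%.
- Total 240: k = 0.01667, R = 1.88 and f = 15.3%.

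The site targets in Section 3.9 are unequal: 60, 60, 116 for two sites together, 24 and 24. I split the 116 as 64:52 by the admissions in Section 3.1 (160:130), which is an assumption. The targets sum to 284, so they are scaled to 192 and 240. Averaged over all 720 site orders:

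| Descriptor ICC (assumed) | Mean R | Flag rate per descriptor | At least one of 13 |
|---|---|---|---|
| 0 | 1.00 | 5% | 49% |
| 0.01 | 1.15-1.19 | 6.8-7.2% | 60-62% |
| 0.05 | 1.75-1.95 | 13.8-16.0% | 85-89% |
| 0.10 | 2.51-2.91 | 21.4-24.8% | 95-97% |

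At ICC 0.05 the per-descriptor rate runs from 9.7% to 21.0% depending on the draw. The last column is the mean over site orders of 1 - (1 - f)^13. At ICC 0 this is 1 - 0.95^13 = 49%. The expected number flagged at ICC 0.05 is 13 × 0.138 = 1.8 to 13 × 0.160 = 2.1.

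The 13 descriptors, all from Section 3.6.3, are age, sex, time post-stroke, lesion location, medical history, NIH-SS, CMSA foot, CMSA leg, MoCA, exercise frequency, exercise intensity, and Schmidt sedentary and recreational time. Questionnaire items are not counted. If descriptors are correlated at 0.3, the chance of at least one flag is 52-54%, 78-83% and 92-95% at ICC 0.01, 0.05 and 0.10.

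**3. Does the rule damage the test?** Simulated type I error with no phase effect, logistic model with random site:

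| Setting | Unadjusted | Rule applied automatically | Fixed set |
|---|---|---|---|
| N = 192, ICC 0.05 | 6.5% | 6.7% | 7.1% |
| N = 240, ICC 0.10 | 9.8% | 8.5% | 9.2% |

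The excess over 5% appears in all three columns, so the rule does not cause it. A separate linear approximation (240 patients, 15 descriptors, 4 of them prognostic, 2,000 trials) gave 4.0%, 3.4% and 3.5%. It gave 5.2% if the smallest p-value among the permitted models was reported.

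**4. Power.** Logistic model, Figure 1 schedule, linear time, outcome and descriptor ICC 0.05, 12 descriptors, three of them in the fixed set, 25% vs 50% active, 1,000 runs per setting. Rule vs fixed set:

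| Prognostic strength (OR per SD) | N = 192 | N = 240 |
|---|---|---|
| none (1, 1, 1) | 74.8 vs 76.4% | 80.9 vs 81.5% |
| moderate (1.5, 1.5, 1.2) | 76.1 vs 77.9% | 82.4 vs 84.6% |
| strong (2.0, 1.5, 1.2) | 75.2 vs 79.9% | 82.6 vs 85.2% |

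The gains are 0.6 to 4.7 points with simulation SE 0.6-1.0, so several are within noise. The linear approximation, with four prognostic covariates, gave 68% vs 73%.

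**5. In-program exercise.** Sections 3.4 and 3.6.1 place collection of the descriptors at enrolment, around the end of the program. Section 3.6.3 includes exercise during out-patient rehabilitation, and Section 3.3 places the program there. Section 3.3.1 adds that in-program exercise is recorded: "Heart rate, blood pressure, rate of perceived exertion, workload, and duration of training will be documented for each session". Section 3.3 also allows exercise before the group: "Prior to starting the group, participants may complete individualized or open-group aerobic exercise as part of their regular in- or out-patient rehabilitation". The chart-review item may therefore mix exercise before and during the program, and Section 3.8 excludes neither. The chart review form (Appendix F) would settle what is extracted, but it is not among the documents available.

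**The case against.** The best defence is that a flag marks a real imbalance in the analysed sample, whatever its cause. With six sites and a random site effect, between-site information still enters the estimate, so such an imbalance can matter. Adjustment is also sensible here because patients enrol after the program and after attendance exclusions that differ by phase (Section 3.4). This stands. The flag rates measure how often the rule is triggered, and the lack of a site term is a weak fault by itself. The fault is choosing covariates by significance and discretion.

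It can also be said that little is lost. That stands too: the simulations show no type I error cost from the automatic rule and only a small power cost. The descriptor ICC is assumed, and the count of 13 includes the two exercise items questioned above. Without them the figure at ICC 0 is 1 - 0.95^11 = 43%.

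A reader might infer that the plan will adjust away part of PROPEL's effect through exercise dose. The documents do not support that. Section 3.6.3 does not say that program sessions are counted, and Section 3.3.2 plans the same group exercise in PROPEL as in GAE. The supportable statement is only that such a variable is not excluded. If PROPEL did change exercise dose, adjusting for it would no longer estimate the total effect.

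**Conclusion.** The point holds as a matter of pre-specification and should be corrected. Section 3.8 refers to the analysis in general. The primary model is covered by that wording but not singled out, and nothing exempts it.

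At an assumed descriptor ICC of 0.05 the screen flags a descriptor with no phase effect in about 14-16% of trials, and at least one of 13 independent descriptors in 85-89%. Even with no clustering the second figure is about 49%, so the conclusion that the covariate list will often be data-driven does not rest on the assumed ICC. It does rest on the descriptor count and, less strongly, on independence between descriptors.

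Two stronger readings should be resisted. One is that the rule inflates type I error: the simulations do not show this when it is applied automatically. The only rise came from deliberately reporting the smallest p-value, and nothing in the plan proposes that. The other is that the rule costs substantial power: the gain from a fixed set is about 1 to 5 points, and the documents do not show how prognostic the covariates are. The eligibility of in-program exercise is a secondary point and depends on what Appendix F extracts.

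**What to change.** Delete the test-then-adjust sentence in Section 3.8 and replace it with wording such as:

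> The primary model will include, regardless of balance, age, sex and pre-stroke physical activity (Schmidt scale), fixed before outcome data are seen. This adjusted analysis is primary. The model with phase, time and random site only is a sensitivity analysis. Cohort descriptors will be summarised by phase and by site, and no significance test will be used to select covariates. Exercise during the GAE or PROPEL program will not enter the primary model.

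The three covariates are an example. The trial team should choose a short prognostic set not plausibly affected by the program. It should also decide in advance whether NIH-SS, CMSA and MoCA belong in the primary model or in a labelled sensitivity analysis. They are measured at enrolment, after the program and the attendance criteria, so phase differences in them may reflect selection. That is a reason to consider them and also a reason for care. If the Schmidt score is used, note that it is recalled after the program; an analysis without it would be reasonable.

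The cost is SAP wording, a few degrees of freedom and one or two extra sensitivity analyses. Every variable is already collected. If the chosen covariates prove not to be prognostic, little power is gained, but the primary model is still defined in advance.

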There is a need to establish strategies to promote long-term uptake of exercise after stroke. Most studies aiming to increase self-directed exercise post-stroke have been implemented in the community after formal rehabilitation is complete. While some community-based programs have reported increased physical activity after the program, many people have difficulty accessing community programs and consequently attendance can be low. The early recovery period during rehabilitation may be an optimal time to not only deliver fitness programming to increase exercise capacity, but also to shape long-term self-directed exercise behaviour. To our knowledge only one group has studied such a program during stroke rehabilitation. This study found that 67% of those who completed the intervention met exercise recommendations, compared to 55% in the control group. However, this study is limited by a non-randomized design, high rates of withdrawal in the intervention group compared to the control group (28% versus 12%), and low rates of compliance with the intervention (<67%). Furthermore, this study included individuals receiving rehabilitation for various conditions and was not focused solely on people with stroke, who have unique challenges to participating in exercise.

We developed Promoting Optimal Physical Exercise for Life (PROPEL) – an exercise and self-management program that aims to facilitate the transition to the community. Our pilot non-randomized study suggests that those who complete PROPEL are more physically active after discharge from rehabilitation than those who do not. The primary aim of this study is to *evaluate the effect of PROPEL delivered during stroke rehabilitation on participation in self-directed exercise after rehabilitation.* Our secondary aims are to evaluate the effect of PROPEL on self-efficacy and outcome expectations for exercise, and barriers to exercise. We hypothesize that, compared to those who

complete group aerobic exercise only, those who complete PROPEL will: 1) be more likely to meet the recommended intensity and duration of self-directed physical activity in the community (i.e.,  $\geq 150$ mins/week of moderate intensity exercise); and 2) report higher self-efficacy and outcome expectations for exercise, and fewer barriers to community activity.

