### 3.9. Sample size

We expect that approximately 25% of people who complete GAE and 50% of individuals who complete PROPEL will be classified as 'active'. A sample of 96 per phase will provide 80% power to detect a 25% to 50% difference at alpha of 0.05 for the 6 sites taking into account an intracluster correlation of 0.05. The sample size calculation was run using PASS Version 12 (Hintze, J, 2014, NCSS, LLC. Kaysville, Utah). We will aim to recruit 120 participants total per phase to account for a conservative 20% drop-out rate; note that in our previous studies where participants were recruited at discharge from rehabilitation and followed for up to 6 months, the rate of withdrawal was much lower (<12%). There are 710 admissions annually to out-patient stroke rehabilitation at all sites combined. We conservatively estimate that approximately 40% of these individuals will be eligible for the study and, of these, 50% will consent to participate. Thus, we expect to recruit ~140 participants annually to meet the target sample size with ~2 years of recruiting (see timelines and milestones: Figure 3). Target sample sizes for each site are: St John's – 60, West Park – 60, Toronto Rehabilitation Institute (both sites) – 116, St Joseph's Care Group – 24, Hamilton Health Sciences – 24.

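### The 6-month-only primary model has no place for a participant missing at 6 months, even one seen at 1 and 4 months, and no missing-data rule is given

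*Combined protocol and SAP*

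**What the plan says.** Section 3.6.1 schedules activity monitoring at 1, 4 and 6 months after the intervention. Section 3.8 sets the primary test: "we will compare the proportion of active and inactive individuals at the final assessment point (6 months post-intervention) using mixed-model logistic regression". Time and phase are the fixed terms and site is the only random term. The 1- and 4-month results are examined as further between-phase comparisons. A similar mixed model is planned for the SSEE, SOEE and BBAQ.

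Section 3.9 (Sample size) assumes that "approximately 25% of people who complete GAE" and "50% of individuals who complete PROPEL" will be active. It states: "A sample of 96 per phase will provide 80% power to detect a 25% to 50% difference". The other inputs are a significance level of 0.05, six sites and a within-site correlation of 0.05. The target rises to 120 per phase "to account for a conservative 20% drop-out rate". The same section reports withdrawal below 12% in the team's earlier studies of this kind.

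Section 3.4 describes repeat calls, a letter and an alternative contact to keep track of participants. No section defines an analysis set, an imputation or weighting rule, or a missing-data sensitivity analysis.

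**The concern.** A model fitted to 6-month status has no record for someone without a 6-month result. With no missing-data rule, the primary analysis becomes an analysis of those observed at 6 months. The outcome is activity itself, and inactive people may plausibly be less willing to wear and return a device for a third week. If loss is related to 6-month activity beyond what time, phase, site and any covariates explain, the phase difference can be biased. The risk is greatest when the amount of loss, or its link to inactivity, differs between GAE and PROPEL. The 1- and 4-month results could reduce that bias, and they are already being collected. The Introduction criticises the one comparable study for unequal withdrawal (28% intervention, 12% control), but the analysis plan contains no provision for the same problem.

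**Working it through.** **1. The plan's own figures.** The inputs from section 3.9 are 25% v 50% active, alpha 0.05 (two-sided assumed), 80% power, intracluster correlation 0.05, 6 sites and 96 per phase.
- Individual-level size, unpooled variance: (1.960 + 0.842)² × (0.25×0.75 + 0.50×0.50) / 0.25² = 54.94 per phase.
- Design effect with 96/6 = 16 per site per phase: 1 + 15×0.05 = 1.75.
- 54.94 × 1.75 = 96.1, so the stated 96 reproduces.
- 96/0.80 = 120 also reproduces. The sizing therefore counts on 96 per phase and allows for 24 of 120 being lost.

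**2. Does "time" bring in the earlier visits?** A similar model is applied to the SSEE and SOEE (measured once, at enrolment) and the BBAQ (once, at 1 month). A visit term would have no meaning there, whereas a study-period term fits a stepped-wedge design. Even if time meant visit, no participant term would link a person's earlier status to month 6, and no phase-by-visit term would isolate the 6-month effect.

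**3. Bias under illustrative drop-out.** These assumptions are not in the documents: true active rates p of 50% (PROPEL) and 25% (GAE) at both 4 and 6 months, all loss after month 4, and loss dependent on 4-month status. With correlation φ between 4- and 6-month status:
- P(active at 6 | active at 4) = p + φ(1−p)
- P(active at 6 | inactive at 4) = p(1−φ)

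Each group is then weighted by its retention.

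*Equal loss, 20% in each phase, inactive twice as likely to leave.* Drop-out (active/inactive) is 13.3%/26.7% in PROPEL and 11.4%/22.9% in GAE.

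*Unequal loss, 28% PROPEL and 12% GAE, inactive 2.5 times as likely to leave.* Drop-out is 16%/40% in PROPEL and 5.6%/14.1% in GAE.

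| φ | Estimated difference, 20%/20% | Odds ratio (true 3.00) | Estimated difference, 28%/12% |
|---|---|---|---|
| 0.3 | 51.25 − 25.80 = 25.4 | 3.02 | 52.50 − 25.54 = 27.0 |
| 0.5 | 52.08 − 26.34 = 25.7 | 3.04 | 54.17 − 25.90 = 28.3 |
| 0.7 | 52.92 − 26.88 = 26.0 | 3.06 | 55.83 − 26.26 = 29.6 |

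*Equal 20% loss, but the link to inactivity may differ by phase.* Here inactive people are three times as likely to leave in the phase or phases named. The scale is a = P(active at 6 | active at 4), the same in both phases.

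| a | Both phases | PROPEL only | GAE only |
|---|---|---|---|
| 0.6 | 24.50 | 26.25 | 23.25 |
| 0.7 | 25.25 | 27.50 | 22.75 |
| 0.8 | 26.00 | 28.75 | 22.25 |
| 0.9 | 26.75 | 30.00 | 21.75 |

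So with a shared mechanism the error is small. With unequal loss it is 2.0 to 4.6 points. With a phase-specific link it is 2.25 to 5.0 points in size for a from 0.7 to 0.9 (1.25 or 1.75 at a = 0.6), and it can go either way.

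**4. Bounds if every drop-out is inactive at 6 months.** Take a 25-point difference among those observed:
- 20%/20%: 0.50×0.80 − 0.25×0.80 = 20 points.
- 28%/12%: 0.50×0.72 − 0.25×0.88 = 14 points.
- 20%/20%, only PROPEL drop-outs inactive: 0.40 − 0.25 = 15 points.
- 12%/12%: 0.50×0.88 − 0.25×0.88 = 22 points.

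**The case against.** A single pre-specified 6-month endpoint is a legitimate primary analysis. The earlier data are analysed in their own right. The 20% is a planning allowance that the protocol calls conservative, earlier studies lost under 12%, and retention is actively managed. At equal 20% loss with a shared two-fold mechanism, the error is at most 1.0 point. The standard error at 96 per phase with design effect 1.75 is far larger: √[0.4375/(96/1.75)] = 8.9 points. All of this stands, and it limits the size of the point.

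The 28%/12% figures also need care. A reader might infer that this trial should expect that imbalance. The documents do not support this: the figures come from a non-randomised study of mixed diagnoses, and the Introduction does not say when those withdrawals occurred. Here participants enrol at the end of the programme, after meeting attendance thresholds, so withdrawal during the programme cannot become post-enrolment drop-out. The scenario is a stress test only.

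Nor would a repeated-measures model cure everything. The all-inactive bounds are missing-not-at-random, and a missing-at-random model would not correct them. Placing all loss after month 4 is also the most favourable case for using earlier visits. A participant random effect would by itself give a participant-specific odds ratio, not the comparison of proportions in section 3.8.

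The objection leaves one gap: the protocol does not say what happens to a missing 6-month outcome.

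**Conclusion.** The point holds in a limited form. As written, the primary model makes no use of 1- and 4-month status for a participant missing at 6 months, and nothing in the protocol fills the gap. Under the stated assumptions, the error on a true 25-point difference is 0.4 to 1.0 point with equal 20% loss and a shared two-fold mechanism. It reaches about 2 to 5 points if loss, or its link to inactivity, differs by phase. It is zero if loss is unrelated to 6-month activity given the model terms. The documents do not establish the direction or the actual size.

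Two stronger readings are not supported. First, a reader might infer that the plan declares a completers-only analysis or discards the earlier visits. It does neither: the exclusion is a default of the model, and the earlier visits have their own comparisons. Second, a reader might infer that the result is valid only if drop-out is unrelated to earlier activity. That is too strict, because loss explained by terms in the model does no harm, and section 3.8 allows covariates. The sample size is not affected.

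**What to change.** In section 3.8, define the primary analysis set as every enrolled participant with at least one follow-up visit, and keep the 6-month phase contrast as primary. Estimate it from a logistic model of active status at 1, 4 and 6 months, with calendar period, visit, phase and phase-by-visit as fixed effects, and with site and participant effects. Report it as a marginal (population-averaged) contrast. The 1- and 4-month contrasts come from the same model. If that model is unstable with 6 sites, apply the planned 6-month model after multiple imputation that uses the earlier visits; state this fallback in advance.

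Keep two sensitivity analyses: the 6-month-only model, and missing counted as inactive, with a range that varies by phase. The second is needed because the primary model cannot address loss that is missing-not-at-random.

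The cost is a change of analysis wording, modest programming and reliance on a missing-at-random assumption. Participants lost before month 1 still contribute nothing. Data collection, sample size and the primary time point do not change.
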